#### Cohort allocation

- Cohort 1: *S. mansoni*-infected children 4 to 6 years of age (n= 150) will be randomized in a 2:1 ratio. Treatment group 1a, n= 100, will be treated with a single dose of 50 mg/kg of L-PZQ ODT (as the test treatment); Treatment group 1b, n= 50, will be treated with the reference PZQ commercial product (Biltricide 600 mg) crushed tablets at a single dose of 40 mg/kg (as the internal control treatment).
- Cohort 2: *S. mansoni*-infected children 2 to 3 years of age (n= 30) will be treated with a single dose of 50 mg/kg of L-PZQ ODT. The primary aim of the descriptive efficacy analysis in this cohort is to explore whether the treatment effect is consistent with the treatment effect in older children (not an independent proof of efficacy in this subgroup).
- Cohort 3: *S. mansoni*-infected infants and toddlers 3 to < 24 months of age (n= 25 to 65) will be treated with a single dose of 50 mg/kg of L-PZQ ODT. The primary aim of the descriptive efficacy analysis in this cohort is to explore whether the treatment effect is consistent with the treatment effect in older children (not an independent proof of efficacy in this subgroup).
- Cohort 4: *S. haematobium*-infected children 3 months to 6 years of age (n= 60) will be treated with a single dose of 50 mg/kg of L-PZQ ODT, to assess the safety and efficacy in this group (not an independent proof of efficacy in this subgroup). After 30 children are enrolled and treated in Cohort 4, the efficacy and safety data will be summarized and evaluated by the IDMC to decide whether there is a need to increase the dose to 60 mg/kg. If a dose increase is needed, 30 additional patients will be added to this cohort (i.e., total sample size of 90 for Cohort 4, n= 60 receiving the final dose) and treated with the 60 mg/kg dose of L-PZQ ODT.

This study is part of the PZQ ODT clinical development program, which aims to register a single dose of L-PZQ ODTs in the targeted pediatric age group (3 months to 6 years of age). The rationale for the design of this study is also based on the information and data gathered from previously conducted Phase I and Phase II studies with the PZQ ODTs (summarized below) and takes into account feedback received from health authorities.

 An Independent Data Monitoring Committee (IDMC) meeting was held on the 09 March 2020 and a decision was made to increase the dose in Cohort 4 to 60 mg/kg.

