#### 4.2.6 Stratification

No stratification for male or female children will be done. It is expected that the number of children with a heavy *S. mansoni* infection will be low in the areas where the study will be conducted. For the moderately-infected children, we expect an overall prevalence of 32% in Ivory Coast and 24% in Kenya (Davis et al., 2015). The participants in Cohort 1 will be stratified, with target enrollment of 40% moderate/heavy infections and 60% light infection.

For Cohorts 2, 3, and 4, no stratification will be implemented. Infants and toddlers in Cohort 3 are only expected to carry light infections.

No stratification for country will be implemented. Each country is expected to contribute at least 10% to the final participant numbers to be included in the final efficacy analysis.

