## 9 Statistical Considerations

### 9.1 Statistical Hypotheses

No formal hypothesis testing is planned. Point estimates of the cure rate and two- sided 95% CI will be calculated for all cohorts.

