In Cohort 2, a total of 30 participants 2 to 3 years of age infected with *S. mansoni* will be enrolled to assess consistency of the treatment effect with that in the older age group. As described in Section 4.2.4, the size of Cohort 2 is 30% of that of Treatment group 1a, to be roughly consistent with the distribution of children 2 to 3 years of age (27%) and 4 to 6 years of age (73%) enrolled in the Phase II study, in which no differences in cure rate by age were observed.

In Cohort 3, overall a total of up to 65 participants 3 to 24 months of age infected with *S. mansoni* will be enrolled in the Phase II and Phase III studies. The sample size in either study alone is too small to have adequate precision on the cure rate, thus the results in this Phase III study (Cohort 3) will be pooled with Cohorts 8 and 9 of the ongoing Phase II study (MS200661-0005). In the Phase II Study MS200661-0005, 20 out of 30 planned participants 13 to 24 months of age and 4 out of 10 planned participants 3 to 12 months of age were enrolled in the study. In Cohort 3 of this Phase III study, at least 25 participants 3 to 24 months of age infected with *S. mansoni* (i.e., ~20% of the total number of participants 2 to 6 years of age receiving L-PZQ ODT) will be enrolled. Since the enrollment of this age group from Phase II was lower than planned, more than 25 participants will be enrolled in Phase III Cohort 3 to achieve a total of 65 participants in this age group. This pooled sample will allow a general comparison to assess whether the treatment effect is similar across age groups.

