### 9.4 Statistical Analyses

All endpoints will be analyzed descriptively. Graphs will be produced as appropriate. Descriptive statistics for categorical endpoints will include frequency counts and percentages. For proportion endpoints, the calculation of 95% CIs will be based on the Clopper-Pearson (exact) method.

Descriptive statistics for continuous endpoints will include: number of available observations, mean, standard deviation, median, lower quartile, upper quartile, minimum, and maximum. For continuous endpoints, the 95% CI around the mean will be calculated where applicable.

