14.3 Supportive Subgroup Analyses for Efficacy Analysis

Analysis set(s):

- Supportive analyses of the primary endpoint will be based on the mITT and PP analysis sets.

Clinical cure rate by subgroup:

If the End of Study Kato-Katz egg count is missing, it will be imputed using the LOCF approach. Subgroup analyses the study will be performed, by the following subgroups:

- Age category (Cohort 4 only)

- Gender
- Severity of infection
- Country

Descriptive statistics of cure rates for each subgroup will be estimated for each cohort.

Cure rate, in terms of proportion of responders, will be summarised by cohort and by infection severity, gender and country and listed by cohort and subject. Estimates of cure rate will be presented graphically in the form of a forest plots presenting point estimates and 95% CIs, by treatment group and subgroup. Forest plot by age group is needed for Cohort 4 only. Cure rates will be presented as percentages, not proportions, i.e. *cure rate* × 100.

For mITT analysis tables will be presented with imputation and without imputation.

15 Safety Analyses

Safety and tolerability assessments:

- Occurrence, nature, severity and outcome of adverse events (AEs),
- Occurrence of treatment-related AEs
- Changes in laboratory safety parameters (hematology, biochemistry, urinalysis) and vital signs (body temperature, blood pressure and pulse rate)

Analysis set(s):

- SAF analysis set.

Safety analyses will be done on the SAF analysis set and according to the as-treated principle. This section includes specifications for summarizing safety endpoints that are common across clinical trials such as AEs, laboratory tests, reactions to the IMP and vital signs.

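### Cohorts 2 and 3 are there to judge whether cure matches that in 4 to 6 year-olds, but the visible plan reports no age difference with an interval, and the infant comparison mixes infection intensities

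*Protocol*

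**What the plan says.** **Aim.** Protocol 4.2 (Cohort allocation) gives Cohorts 2 and 3 the same purpose: to "explore whether the treatment effect is consistent with the treatment effect in older children (not an independent proof of efficacy in this subgroup"). Protocol 9.2 repeats it for the 3 to 24 month sample pooled with Phase II: "This pooled sample will allow a general comparison to assess whether the treatment effect is similar across age groups".

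**Planned outputs.** Protocol 9.1 states: "Point estimates of the cure rate and two- sided 95% CI will be calculated for all cohorts". It also states: "No formal hypothesis testing is planned". Protocol 9.4 fixes the method: "For proportion endpoints, the calculation of 95% CIs will be based on the Clopper-Pearson (exact) method". SAP 14.1 and 14.2 implement this with forest plots. For the subgroups, which include severity of infection, SAP 14.3 says: "Descriptive statistics of cure rates for each subgroup will be estimated for each cohort".

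**Pooled infants.** Protocol 9.4.1 names a logistic model adjusted for study and site. Its purpose is to estimate the infants' cure rate, not to compare them with older children. SAP 14.2.1 does not mention that model. It places the pooled infants in additional tables apart from the main study table.

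**Infection intensity.** Cohort 1 targets 40% moderate/heavy and 60% light infections (Protocol 4.2.4, 4.2.6). Of Cohort 3, Protocol 4.2.6 says: "Infants and toddlers in Cohort 3 are only expected to carry light infections". Cohort 2 takes both severities without stratification (4.2.4).

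**The concern.** The question for Cohorts 2 and 3 is a comparison, but the visible outputs are one-sample estimates. A reader who has to judge similarity will set two intervals side by side. Overlap of two 95% intervals is a much blunter instrument than an interval for the difference, and it does not show how large a loss remains possible. Protocol 9.2 quantifies precision for groups 1a and 1b and for Cohort 4, but not for Cohort 2, Cohort 3 or any age contrast.

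The infant comparison has a second problem. If lighter infections are cured more often, a light-only infant group is flattered when set against a mixed older group.

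At stake is how firmly the report can describe cure below 4 years as consistent with cure at 4 to 6 years. Those ages have no randomised control.

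**Working it through.** **1. Reproduce the plan's own figure.** The exact limits are the Beta(x, n-x+1) quantile at 0.025 and the Beta(x+1, n-x) quantile at 0.975. For 82/95 the lower limit is 77.7%, as in Protocol Table 5. For 36/43 the limits are 69.3% to 93.2%, as in Protocol 9.2.

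**2. Inputs.**
- Group 1a: mITT n = 95 (Protocol 9.2).
- Cohort 2: 30 enrolled. Applying the 5% malaria exclusion here too (an assumption), 0.95 x 30 = 28.5, taken as 28.
- Pooled 3 to 24 months: 65 planned; 0.95 x 65 = 61.75, taken as 62.
- Phase III Cohort 3 alone: Phase II enrolled 20 + 4 = 24, so 65 - 24 = 41; 0.95 x 41 = 38.95, taken as 39.
- True cure in 1a: 85%, an assumption that lies between Table 5's 80.0% and 86.3%.
- True losses of 10, 15 and 20 points in the younger group: assumptions. The documents define no relevant loss.

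**3. Chance that a true loss goes unseen.** Sum Bin(x1; 95, 0.85) x Bin(x2; n2, 0.85 - loss) over all outcomes where (a) the two exact 95% intervals overlap, or (b) the Newcombe 95% interval for 1a minus younger has a lower limit at or below 0.

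| True loss | Cohort 2 (28): overlap | Cohort 2: difference CI misses | Pooled infants (62): overlap | Pooled: difference CI misses |
|---|---|---|---|---|
| 10 points | 96% | 75% | 93% | 65% |
| 15 points | 88% | 56% | 77% | 39% |
| 20 points | 75% | 37% | 52% | 17% |

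Sensitivity for the 15-point loss, with 1a at 86.3% and then 80%: overlap is 87% and 90% for Cohort 2, and 75% and 81% for the infants (n = 61). The difference interval misses in 55% and 62%, and in 37% and 45%.

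**4. What equal observed rates would leave open.** With d = p1 - p2 and Wilson limits (l, u), the Newcombe limits are d - sqrt[(p1-l1)^2 + (u2-p2)^2] and d + sqrt[(u1-p1)^2 + (p2-l2)^2]. For 1a, 81/95 = 85.3% (Wilson 76.8 to 91.0).
- Cohort 2, 24/28 = 85.7% (68.5 to 94.3): -12.5 to +17.7 points.
- Pooled infants, 53/62 = 85.5% (74.7 to 92.2): -11.0 to +12.0 points.
- Cohort 3 alone, 33/39 = 84.6% (70.3 to 92.7): -11.1 to +16.1 points.

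**5. Infection intensity.** The documents give no cure rate by intensity, so both direction and size are assumed. If light infections are cured g points more often, crude 1a cure lies 0.40 x g below light 1a cure. For g = 10 to 20, a light-only infant group could be 4 to 8 points worse like for like and still match the crude 1a rate.

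**6. Light-only comparator.** The target mix leaves 0.60 x 95 = 57 light-infected children in 1a. For 49/57 = 86.0% (Wilson 74.7 to 92.7) against 53/62, the interval is -12.6 to +13.2 points. Like-for-like precision therefore costs little. With 85% light cure and a 15-point loss, the difference interval misses in 49% of trials, against overlap in 84%.

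**The case against.** - **No overlap rule is in the plan.** The documents speak only of exploring and of a general comparison. A reader might infer that a relevant loss would usually pass as consistency. The documents do not support that as a general statement. It presumes the overlap reading, and even then a 20-point loss in the pooled infants is near even (52%).
- **The aim is descriptive.** Independent proof of efficacy is disclaimed and nothing is tested. This stands. A difference with an interval is equally descriptive.
- **Severity subgroups are already planned.** Protocol 9.4.1 and SAP 14.3 give cure by cohort and severity with intervals, so light-infected 1a children can be set beside Cohort 3. This narrows the gap to the missing difference and interval.
- **A reader could compute the difference from the reported counts.** True for the crude contrast, but then neither the method nor the comparator is fixed beforehand.
- **The pooled contrast crosses studies.** SAP 14.2.1 equates a Phase II visit at days 14 to 21 with days 17 to 21 here, and a simple difference drops the protocol's study and site adjustment. This stands, and is why Cohort 3 alone should also be shown.
- **The intensity point is uneven.** A reader might infer that all the younger cohorts differ in intensity by design. Only Cohort 3 does, and only as an expectation. Cohort 2 is uncontrolled.
- **Phase II.** Protocol 9.2 refers to children "enrolled in the Phase II study, in which no differences in cure rate by age were observed". A reader might infer that this already misuses small numbers, since 36/43 at 4 to 6 years and the overall 86% (74% to 94%) imply only 8 to 14 younger children at 45 mg/kg. The statement, however, covers the whole study: 420 randomised, 27% of those enrolled aged 2 to 3, or about 0.27 x 420 = 113. The back-calculation also rests on rounded figures. The inference is not supported.

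**Conclusion.** The point holds in limited form. The visible plan sets an age-consistency question for Cohorts 2 and 3 and provides no age difference with an interval. For the infants, the crude contrast with 1a also mixes infection intensities. If similarity were read from overlapping intervals, a true 15-point loss from 85% would be compatible with overlap in about 88% of trials for Cohort 2 and 77% for the pooled infants. A difference interval would miss it in about 56% and 39%. That is clearly better, though still far from decisive.

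This rests on an assumed 85% cure in 1a, the 5% exclusion applied to every cohort, and full recruitment. The 4 to 8 point intensity effect is purely illustrative. Some text near the secondary endpoint table in Protocol 9.4.1 and under the significance level in SAP section 9 is redacted, so the statement is that no such difference is visible, not that none exists.

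A reader might also infer that registration below 4 years rests on this comparison alone. The documents do not say so: egg reduction, POC-CCA and PK data are collected in these ages too. This is an inexpensive improvement to the analysis, not a flaw in the primary result.

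**What to change.** In SAP 14.2 and 14.2.1, add two descriptive cure-rate differences: 1a minus Cohort 2, and 1a minus pooled 3 to 24 months. Give each a two-sided 95% interval (Newcombe or Miettinen-Nurminen).

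- Report each one crude and accounting for baseline intensity: stratified by light versus moderate/heavy for Cohort 2, and with light-infected 1a children as the comparator for the infants.
- Show the infant contrast also for Phase III Cohort 3 alone, because the pooled one crosses studies.
- State that consistency is described by the upper limit of the interval, meaning the largest loss not excluded. Use no test and no fixed margin.

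The cost is some SAP wording and one extra table from data already collected. The intervals will be wide, so the consistency statement will read as less firm, and the light-only comparison uses about 57 rather than 95 children from 1a.

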### 9.3 Populations for Analyses

The analysis populations are specified below, in Table 6. The final decision to exclude participants from any analysis population will be made during a blinded data review meeting prior to database lock.

**Table 6** Analysis populations

| Population                  | Description  |
|-----------------------------|--|
| Enrolled                    | All participants who sign informed consent.  |
| Intention-to-treat          | The Intention-to-Treat (ITT) Analysis Set will include all participants enrolled.  |
| Modified Intention-To-Treat | Modified intention-to-treat (mITT) Analysis Set includes all enrolled participants who receive one dose of treatment and who have baseline measurement. Children who require malaria treatment after enrollment in the study will not be included in the mITT Analysis Set. The primary analysis of this study will be performed on the mITT Analysis Set.   |
| Per-Protocol                | Per-protocol (PP) Analysis Set includes all participants who are in the mITT population and have one post baseline measurement without any clinically important protocol deviations. Details of the criteria for exclusion from the PP population will be provided in the Statistical Analysis Plan planned to be finalized before first participant being dosed. An additional determination will be made prior to database lock, based on a review of data (without knowledge of treatment assignment for Cohort 1) accrued during the conduct of the study. |
| Safety                      | The Safety Analysis Set will include all participants who receive a dose of study treatment. Participants will be analyzed according to the actual treatment they receive.   |

### 9.4 Statistical Analyses

All endpoints will be analyzed descriptively. Graphs will be produced as appropriate. Descriptive statistics for categorical endpoints will include frequency counts and percentages. For proportion endpoints, the calculation of 95% CIs will be based on the Clopper-Pearson (exact) method.

Descriptive statistics for continuous endpoints will include: number of available observations, mean, standard deviation, median, lower quartile, upper quartile, minimum, and maximum. For continuous endpoints, the 95% CI around the mean will be calculated where applicable.

#### 9.4.1 Efficacy Analyses

The primary efficacy analysis will be performed on the mITT population of Cohort 1. The primary endpoint of cure rate will be calculated as the percentage of egg-positive participants at baseline who become egg-negative after treatment (as assessed by the Kato-Katz method). The exact 95% CI will be calculated based on the Clopper-Pearson method. Cohorts 2, 3, and 4 will be analyzed similarly.

The secondary endpoint of cure rate by POC-CCA® (Cohorts 1, 2, and 3) will be analyzed in the same manner as the primary endpoint, with proportion cured and its 95% CI.

The secondary endpoint of ERR will be analyzed for each of the cohorts and treatment group (Cohort 1) as group-based ERR (arithmetic and geometric) and as individual ERR (arithmetic and geometric).

Subgroup analyses will also be conducted by severity of infection (light vs. moderate/heavy infection stratification factor), country and gender. In Cohort 4, subgroup analyses will also be done by specific age groups (e.g., 3 months to 24 months of age, 2 to < 4 years of age, 4 to 6 years of age).

Sensitivity analyses may be performed on the ITT population of Cohort 1, to determine the impact of participants requiring malaria treatment, and on the PP population of Cohort 1, to assess the impact of any protocol deviations (such as completing study assessments outside the Day 17 to 21 window).

Analysis of Cohort 3 will be a pooled analysis, including the mITT population from this study and the mITT population for participants 3 to 24 months of age in the Phase II study MS200661-0005 (Cohorts 8 and 9). A logistic regression model with adjustment for study and site variability will be used to estimate cure rate.

Analysis of Cohort 4 will be performed only on the mITT population and using the same methods as for Cohort 1.

Imputation will be needed for participants in the mITT Analysis Set but not in the PP Analysis Set. For continuous endpoints, the imputation method of last observation carried forward will be used for missing data at the post baseline measurement. For binary endpoints, the imputation method of worst case will be used for missing data at the post baseline measurement. The baseline egg count for participants with missing follow-up egg count will be carried forward for both ERR and cure rate calculations, such that these participants will be considered “no change” and “not cured”, respectively, for purposes of the efficacy analysis. This is equivalent to the “missing = non-responder” approach. For the 60 mg/kg dose group in Cohort 4, if egg count at Extended Follow-up is missing, egg count from End of Study visit will be carried forward for cure rate and ERR calculation in the analyses with imputation.

Sensitivity analyses will be performed to understand the impact of missing data on the primary and secondary endpoints.

| Efficacy Endpoint | Statistical Analysis Methods  |
|-------------------|---|
| Primary           | Cure rate as assessed by the Kato-Katz method for Cohort 1  |
| Secondary         | Cure rate as assessed by the Kato-Katz method for Cohorts 2 and 3.
Cure rate as assessed by the POC-CCA method for Cohorts 1, 2, and 3.
Cure rate as determined by urine filtration technique for Cohort 4.
ERR from pretreatment to 17 to 21 days after treatment using Kato-Katz method for Cohorts 1, 2, and 3.
ERRs from pretreatment to 17 to 21 days and 35 to 40 days after treatment using urine filtration technique for Cohort 4. |
| CCI               |   |

#### 9.4.2 Safety Analyses

All safety analyses will be performed on the Safety Analysis Set, which will include all participants who receive a dose of study treatment. Participants will be analyzed according to the actual treatment they receive.

Values for all safety variables will be listed by subject and time point. Safety variables will be summarized using descriptive statistics by cohort and by treatment group (for Cohort 1).

AEs will be coded by the Medical Dictionary for Regulatory Activities (MedDRA) preferred terms, and all summary tables for AEs will be organized by these categories. Frequency counts and percentages will be presented for subjects with at least 1 TEAE within each System Organ Class (SOC) and preferred term, separated by treatment group and cohort. TEAEs will also be summarized by relationship to treatment and by severity within each cohort and treatment group (for Cohort 1).

By-patient listings of clinical laboratory data and vital signs will include indications of values that are outside the reference ranges, and values that are clinically significant. Tables describing out-of-reference range shifts will be provided for clinical laboratory test results and vital signs as appropriate and by treatment arm.

#### 9.4.3 Other Analyses

Demographic data including age, gender, height, medical history and previous medication will be provided in by-patient listings and summarized by cohort and treatment group (for Cohort 1).

PK parameters and calculations have been detailed in Section 8.5. PK analysis will also be specified in the Integrated Analysis Plan that will be finalized before database lock.

Estimation of Individual PK Parameters:

- Pharmacokinetic parameters will be calculated by the PK/PD Data Processing Group of QP, Merck, Darmstadt, Germany, or by a Contract Research Organization (CRO) selected by the Sponsor, using standard non-compartmental methods and the actual administered dose. PK parameters will be calculated using the actual elapsed time since dosing, given with a precision of 14 significant digits or the SAS format Best12. When the actual sampling time is missing, calculations will be performed using the scheduled time. Otherwise, there will be no further imputation of missing data. The actual collection intervals will be used in the calculation of urine and fecal parameters.
- Non-compartmental computation of pharmacokinetic parameters will be performed using the computer program Phoenix® WinNonlin® version 6.3, or higher (Certara, L.P., [name]).
- The statistical software SAS® (Statistical Analysis System, SAS-Institute, Cary NC, USA, windows version 9.1 or higher) may be used to produce tables, listings and figures and in the calculation of PK parameters if appropriate.

No other analyses are planned.

